- a Start-of-Treatment/Enrollment (Combined V1/V2) Visit for patients from PDY14192, EFC13579, and EFC13691 studies, after having performed the assessments of *end-of-treatment visit in the parent study*. Visit windows for subsequent visits are ± 3 days in the first 12 weeks and ± 1 week for the remainder of the study.
- b Patients who discontinue treatment early are scheduled, as soon as possible, for the EOT Visit, followed by the EOS Visit. If LTS12551 is terminated, then the next visit for all involved patients will be the EOT Visit, followed by the EOS Visit.
- c Eligible patients in PDY14192, EFC13579, and EFC13691 studies should rollover into LTS12551 the same day as the *end-of-treatment visit of the parent study*. Visit 1 and Visit 2 of LTS12551 study should be combined with the *end-of-treatment visit of the PDY14192, EFC13579 or EFC13691 parent studies*.
- d Chest imaging: Chest X-ray, MRI or HRCT will be performed only if no chest imaging results obtained within the previous 12 months are available. At the Investigator's discretion (and based on local regulations) chest imaging may be performed during the study (eg, 1 year after the last chest imaging assessment or after a year's treatment).
- e Every 2 weeks (q2w) the IMP administrations must be separated by at least 11 days. The treatment period visits occur q2w up to Visit 8 (Month 3), every month up to Visit 11 (Month 6), and every 3 months for the remaining duration of the study. For IMP administrations coinciding with treatment period visits, patients will be monitored at the study site for a minimum of 30 minutes after injections. If the patient or the Investigator decides not to administer IMP at home, the injections can be performed at the study site by way of unscheduled visits.
- f The injection training is for patients who are willing to perform self-injection. The Investigator or delegate should review the patient's self-administration technique at the Combined V1/V2 Visit.
- g Electronic diary / PEF meter will no longer be used in this study due to Amendment 04 (see [Section 10.6](#)).

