9.2.2.8 Prescribed oral corticosteroids (OCS) dose for patients from the EFC13691 study

For patients from EFC13691 the prescribed background therapy with OCS will be recorded in the e-CRF.

For the patients from the EFC13691 study only, the following 3 efficacy endpoints will be derived using the prescribed dose of the background OCS medications. The baseline OCS dose is the original baseline value from the EFC13691 study.

- Percentage change from baseline in OCS dose;
- Proportion of patients achieving a reduction of 50% or greater in their OCS dose compared with the original baseline in the parent study;
- Percentage of patients that were able to be tapered off completely of OCS.

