10.3.4 Handling of patients after permanent treatment discontinuation

Patients will be followed-up according to the study procedures as specified in this protocol up to the scheduled date of study completion, or up to recovery or stabilization of any AE to be followed-up as specified in this protocol.

After the permanent discontinuation of dupilumab, the patients will be assessed using the procedure normally planned for the EOT Visit. After 12 weeks follow-up time, the patients will be asked to return for the EOS assessments.

All cases of permanent treatment discontinuation should be recorded by the Investigator in the appropriate pages of the CRF when considered as confirmed.

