11.4.2 Analyses of efficacy endpoints

There will be no confirmatory analysis for the efficacy variables. All analyses will be done descriptively on the safety population in observed case, as appropriate. The baseline value for the applicable efficacy parameters is the original baseline from the parent studies.

For the continuous efficacy variables, descriptive statistics (number, mean, SD, median, minimum and maximum) will be presented for the parameter and its change from baseline over visits. In addition, a figure of mean change from baseline (with corresponding standard error) will be presented for the continuous efficacy parameter over visits.

For the categorical efficacy variables, the number and percentage will be presented over time for all patients who have data available at that time point.

For severe exacerbation events, the total number of severe exacerbation events, total patient-years, unadjusted annualized severe exacerbation event rate, and individual patient annualized severe exacerbation event rate (number, mean, SD, median, minimum and maximum) during the treatment period will be summarized.

More details about the efficacy analysis can be found in the SAP.

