2.4.4 Analyses of efficacy endpoints

There will be no confirmatory analysis for the efficacy variables. All analyses will be done descriptively on the safety population in observed case, as appropriate. The baseline value for efficacy parameters is the original baselines from the parent studies.

For severe exacerbation events, the number of patients with one or more severe exacerbation events (number and qualitative variable: Yes/No), number of severe exacerbation events (qualitative variable: 0, 1, 2, 3, \geq 4), total number of severe exacerbation events, total patient-years, unadjusted annualized severe exacerbation event rate, and individual patient annualized severe exacerbation event rate (number, mean, SD, median, minimum, maximum) will be presented by the treatment category and overall (see Section 2.3.2) during the treatment period. Number and annualized rate will also be analyzed for severe exacerbation with use of systemic corticosteroids for \geq 3 days only, and that with hospitalization or with emergency room visit only. The mean duration of a severe exacerbation will also be summarized.

For the continuous efficacy variables listed in Section 2.1.3, descriptive statistics (mean, SD, median, minimum and maximum) will be presented for the parameter and its change from baseline over visits and by the treatment category and overall (see Section 2.3.2). In addition, figure of mean change from baseline (with corresponding standard error) will be presented for the continuous efficacy parameter over visits and by the treatment category and overall (see Section 2.3.2).

For the categorical efficacy variables listed in Section 2.1.3, the number and percentage will be presented over time for all patients who have data available at that time point by the treatment category and overall (see Section 2.3.2).

In addition, particularly for the patients coming from the EFC13691 study, the descriptive statistics (mean, SD, median, minimum and maximum) for the percentage change from baseline in oral corticosteroids (OCS) dose will be presented over time by the treatment category and overall (see Section 2.3.2); and, the proportion of patients achieving a reduction of 50% or greater in their OCS dose compared with the original baseline in parent study, and the proportion of patients whose background OCS are completely tapered off will be presented over time by the treatment category and overall (see Section 2.3.2).

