- For quantitative safety parameters based on central laboratory/reading measurements, descriptive statistics will be used to summarize results and change from baseline values by visit and treatment category and overall (see Section 2.3.2). Summaries will include the endpoint value and/or the worst on-treatment value. The endpoint value is commonly defined as the value collected at the date of last IMP dose + 14 days or the end of treatment visit. If this value is missing, this endpoint value will be the closest value prior to the last administration of IMP + 14 days. The worst value is defined as the nadir and /or the peak post-baseline (up to last administration of IMP + 14 days) according to the direction (minimum or maximum) of the abnormality as defined in the PCSA list.
- All of the values including unscheduled measurements will be assigned to the appropriate safety analysis visit window. The safety analysis visit window is defined in Section 2.5.4.
- The analysis of the safety variables will be essentially descriptive and no systematic testing is planned.

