2.5.3 Missing data

For categorical variables, patients with missing data are not included in calculations of percentages unless otherwise specified. When relevant, the number of patients with missing data is presented.

Handling of computation of treatment duration if investigational medicinal product end of treatment date is missing

For the calculation of the treatment duration, the date of the last dose of IMP is equal to the date of last administration reported on the end-of-treatment case report form page. If this date is missing, the exposure duration should be left as missing.

The last dose intake should be clearly identified in the case report form and should not be approximated by the last returned package date.

Handling of medication missing/partial dates

No imputation of medication start/end dates or times will be performed. If a medication date or time is missing or partially missing and it cannot be determined whether it was taken prior or concomitantly, it will be considered a prior and concomitant medication.

Handling of adverse events with missing or partial date/time of onset

Missing or partial adverse event onset dates and times will be imputed so that if the partial adverse event onset date/time information does not indicate that the adverse event started prior to treatment or after the treatment-emergent adverse event period, the adverse event will be classified as treatment-emergent. No imputation of adverse event end dates/times will be performed. These data imputations are for categorization purpose only and will not be used in listings. No imputation is planned for date/time of adverse event resolution.

Handling of adverse events when date and time of first investigational medicinal product administration is missing

When the date and time of the first IMP administration is missing, all adverse events that occurred on or after the day of randomization should be considered as treatment-emergent adverse events. The exposure duration should be kept as missing.

The last dose intake should be clearly identified in the case report form and should not be approximated by the last returned package date.

Handling of missing assessment of relationship of adverse events to investigational medicinal product

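### ACQ-5/AQLQ responder and OCS-reduction percentages are taken over patients with data at each visit, so they may be overstated, and may rise, if patients who stop dupilumab early succeed less often than those who stay

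*SAP*

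**What the plan says.** **Denominator.** Protocol 11.4.2 sets the approach: "All analyses will be done descriptively on the safety population in observed case, as appropriate". SAP 2.4.4 repeats it and, for categorical efficacy variables, adds that "the number and percentage will be presented over time for all patients who have data available at that time point". SAP 2.5.3 gives the general rule: "For categorical variables, patients with missing data are not included in calculations of percentages unless otherwise specified". Nothing is specified otherwise for these endpoints. On disclosure it says only: "When relevant, the number of patients with missing data is presented".

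**Endpoints covered.** SAP 2.1.3 lists ACQ-5 and AQLQ responder status and, for patients from EFC13691, the proportion with an OCS reduction of 50% or more and the proportion tapered off. Protocol 9.2.2.8 words the last one as "Percentage of patients that were able to be tapered off completely of OCS". SAP Appendix B enters No under supportive analysis for every efficacy endpoint.

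**Visits after an early stop.** Footnote b of the flow charts (Protocol 1.2 and 1.3) reads: "Patients who discontinue treatment early are scheduled, as soon as possible, for the EOT Visit, followed by the EOS Visit". Protocol 10.3.4 says: "After 12 weeks follow-up time, the patients will be asked to return for the EOS assessments". The same section also says that follow-up runs to the scheduled date of study completion.

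**Safety tables.** For quantitative safety parameters, SAP 2.4.5 adds an endpoint row: "The endpoint value is commonly defined as the value collected at the date of last IMP dose + 14 days", or at the EOT visit, falling back to the closest earlier value. The efficacy tables have no such row.

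**The concern.** A secondary objective is long-term efficacy in patients who came from the parent studies. A percentage taken over patients with data at a visit describes mainly those who have stayed on dupilumab. Patients who leave because of poor control or an adverse event disappear from both numerator and denominator at later on-treatment visits. A responder or OCS-free percentage that climbs over time could then be read as sustained or growing benefit when only the mix of patients has changed. No planned efficacy row would let a reader separate the two. SAP Section 3 has all planned analyses run for the asthma submission, so these tables will be used.

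**Working it through.** The documents give no responder rate, discontinuation rate or sample-size calculation for these endpoints, so there is no stated figure to reproduce. The check has three parts.

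**1. Where early stoppers fall in the windows (SAP 2.5.4, Table 6)**

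- ACQ-5 and AQLQ have two post-baseline windows: Week 24 (days 2 to 252) and Week 48 (day 253 onward).
- In the 48-week cohort the EOT visit includes both questionnaires (Protocol 10.1.2.12). An early EOT before day 253 counts at Week 24 and is absent at Week 48. An early EOT on day 253 or later still counts at Week 48.
- In the 96-week cohort the EOT visit includes neither questionnaire (Protocol 1.2 and 10.1.1.16). A patient who stops between the Week 24 and Week 48 visits has a Week 24 value only.
- Prescribed OCS dose has a window at every visit to Week 96, so losses accumulate. The EOS row, from the day after the end of treatment, takes early stoppers back in, but off treatment.
- After Week 48 the OCS denominator also falls by design, because patients enrolled after Amendment 04 finish treatment then. The dropout effect has to be judged within one planned duration.

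**2. Observed-case against all-starters percentage**

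Let d be the fraction stopped before the visit, p the stayers' success rate and rp the stoppers' rate. The observed-case percentage is p. The all-starters percentage is (1-d)p + d·r·p = p(1-d(1-r)). The ratio is 1/(1-d(1-r)). Both d and r are assumed.

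| d | r = 0 | r = 0.5 | r = 1 |
|---|---|---|---|
| 10% | 1.111 | 1.053 | 1.000 |
| 20% | 1.250 | 1.111 | 1.000 |
| 30% | 1.429 | 1.176 | 1.000 |

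A 10% relative overstatement needs d = (1-1/1.1)/(1-r), which is 9.1% for r = 0 and 18.2% for r = 0.5.

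**3. Can the percentage move with no patient changing status?**

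Take N = 210, the number randomized in EFC13691 (SAP 1.1) and so an upper bound for the OCS endpoints. Assume an early rate of 105/210 = 50.0% and freeze every patient's status.

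| Success among leavers | 10% stop (n=189) | 20% stop (n=168) | 30% stop (n=147) |
|---|---|---|---|
| 0% | 105/189 = 55.6% | 105/168 = 62.5% | 105/147 = 71.4% |
| 25% | 100/189 = 52.9% | 95/168 = 56.5% | 89/147 = 60.5% |
| 50% | 95/189 = 50.3% | 84/168 = 50.0% | 73/147 = 49.7% |
| 60% | 92/189 = 48.7% | 80/168 = 47.6% | 67/147 = 45.6% |

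The percentage rises if leavers succeed less often than stayers, stays flat apart from rounding if they succeed equally often, and falls if they succeed more often.

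**The case against.** The strongest reply is that this is a single-arm, open-label safety extension with no confirmatory efficacy analysis. Protocol and SAP agree on observed case, and the objective names no all-starters strategy. Context is already planned: discontinuations by main reason (SAP 2.2), exposure categories (SAP 2.4.3.1), and exacerbation rates that use each treated patient's on-treatment time (SAP 2.1.3.1). All this stands and is why the observed-case rows should stay. It does not remove the point, because none of those summaries shows what the responder or OCS percentage would be if leavers were kept in.

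A reader might infer three stronger things that the documents do not support.

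- That the rates are overstated as a matter of fact. Without a discontinuation rate or the outcome status of leavers, the direction is unknown and can reverse.
- That ACQ-5 and AQLQ rates could drift to Week 96. Week 48 is their last window.
- That early stoppers are missing from every later row. Late EOT questionnaires in the 48-week cohort and the OCS EOS row are exceptions.

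It is also fair to object to making a non-responder count the main figure. At 20% stopping, with leavers succeeding as often as the whole cohort (50%), it gives 84/210 = 40.0% against an observed 84/168 = 50.0%. The observed-case rate exceeds such a count by the factor 1/(1-d) whatever the leavers' status, so the count builds in a bias the other way.

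**Conclusion.** The point holds conditionally. The denominator rule, its reach to the four percentages and the loss of early stoppers from later on-treatment rows are in the text. Overstatement follows only if stoppers succeed less often than stayers. On that assumption, with 10% to 20% stopping and r between 0 and 0.5, the relative excess is 5% to 25%. At r = 1 there is none. The primary safety endpoint is unaffected. The working takes follow-up after a stop as EOT plus a 12-week EOS, as the flow-chart footnotes and Protocol 10.3.2 describe. The two follow-up statements in Protocol 10.3.4 need reconciling.

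**What to change.** Keep the observed-case rows as planned and show n and number missing at each visit. SAP 2.4.4 leaves the number of patients out of its continuous-variable statistics, although Protocol 11.4.2 includes it. Then:

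1. In SAP 2.4.4 and Appendix B, add a sensitivity percentage, not the headline figure, for ACQ-5 responder, AQLQ responder, OCS reduction of 50% or more, and OCS tapered off.
   - Denominator: safety-population patients assessable for the endpoint, whose planned duration includes the visit and who could have reached it by the data cut-off. Assessable means a validated translation is available for the questionnaires, PDY14192 is excluded for AQLQ, and EFC13691 only for OCS.
   - Patients who permanently stopped dupilumab before the visit count as not achieving the endpoint.
   - Patients still on drug with no value are shown in a separate missing category.
   - Name this row in SAP 2.5.3 as an exception to the general rule.
2. Add to the FEV1 and OCS-dose tables the endpoint row (EOT or last on-treatment value) from SAP 2.4.5.
3. Reconcile the two follow-up statements in Protocol 10.3.4.

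The cost of items 1 and 2 is SAP wording and a few table rows, from data already collected. The small downside is that the sensitivity figure is conservative for patients who stop for reasons unrelated to efficacy. With both rows shown, the reader can see how far the result depends on who stayed.

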2.4.4.1 Subgroup analyses

Subgroup analyses will be performed for several key efficacy variables (severe exacerbation events, FEV1, ACQ5, and AQLQ) by:

- ICS dose group: patients on the medium or high ICS dose at the original baseline in the parent studies
- Blood eosinophil (Giga/L) groups at baseline of the parent study: ≥0.3, <0.3, ≥0.15, <0.15, ≥0.15 <0.3, ≥0.3 <0.5, and ≥0.5

2.4.4.2 Multiplicity issues

Not applicable.

2.4.5 Analyses of safety data

The summary of safety endpoints will be presented by the treatment category and overall (see Section 2.3.2).

General common rules

All safety analyses will be performed on the safety population as defined in Section 2.3.2, unless otherwise specified, using the following common rules:

- The baseline value for safety parameters is defined as the original baseline from the parent studies.
- In addition to the baseline values, the pre-dose measurements at Week 0 in LTS12551 will be presented in the by-visit summary/figure for laboratory, vital signs or ECG parameters. The pre-dose measurements at Week 0 of LTS12551 are defined as follows: for patients enrolled from DRI12544, the measurements at Week 0 are obtained from the EOS visit of DRI12544 if available, regardless whether the EOS visit in DRI12544 was combined with Visit 1/Visit 2 in LTS12551; otherwise, Week 0 value will be the last available measurement prior to the first IMP dose in LTS12551 study. For patients enrolled from the EOT visit of parent studies if available; otherwise, Week 0 value will be the last available measurement prior to the first IMP dose in LTS12551 study. For patients enrolled from the EOT visit of parent studies if available; otherwise, Week 0 value will be the last available measurement prior to the first IMP dose in LTS12551 study.
- The potentially clinically significant abnormality (PCSA) values are defined as abnormal values considered medically important by the sponsor according to predefined criteria/thresholds based on literature review and defined by the sponsor for clinical laboratory tests, vital signs, and ECG (Appendix A).
- PCSA criteria will determine which patients had at least one PCSA during the treatmentemergent adverse event period, taking into account all evaluations performed during the treatment-emergent adverse event period, including non-scheduled or repeated evaluations.

The number of all such patients will be the numerator for the on-treatment PCSA percentage.

- The treatment-emergent PCSA denominator for a given parameter will be based on the number of patients assessed for that given parameter in the treatment-emergent adverse event period by the treatment category and overall (see Section 2.3.2) on the safety population.
- For quantitative safety parameters based on central laboratory/reading measurements, descriptive statistics will be used to summarize results and change from baseline values by visit and treatment category and overall (see Section 2.3.2). Summaries will include the endpoint value and/or the worst on-treatment value. The endpoint value is commonly defined as the value collected at the date of last IMP dose + 14 days or the end of treatment visit. If this value is missing, this endpoint value will be the closest value prior to the last administration of IMP + 14 days. The worst value is defined as the nadir and /or the peak post-baseline (up to last administration of IMP + 14 days) according to the direction (minimum or maximum) of the abnormality as defined in the PCSA list.
- All of the values including unscheduled measurements will be assigned to the appropriate safety analysis visit window. The safety analysis visit window is defined in Section 2.5.4.
- The analysis of the safety variables will be essentially descriptive and no systematic testing is planned.

2.4.5.1 Analyses of adverse events

Generalities

The primary endpoint of this study is the number (n) and percentage (%) of patients experiencing any treatment-emergent adverse events (TEAE). Pre-treatment (if applicable) adverse events will be described separately.

If an adverse event date/time of onset (occurrence, worsening, or becoming serious) is incomplete, an imputation algorithm will be used to classify the adverse event as pre-treatment or treatmentemergent adverse event. The algorithm for imputing date/time of onset will be conservative and will classify an adverse event as treatment-emergent, unless there is definitive information to determine it is pre-treatment. Details on classification of adverse events with missing or partial onset dates are provided in Section 2.5.

Adverse event incidence tables will be presented by system organ class (SOC), high level group term (HLGT), high level term (HLT) and preferred term (PT) sorted in alphabetical order, to summarize the number (n) and percentage (%) of patients experiencing at least an AE by the treatment category and overall (see Section 2.3.2). Multiple occurrences of the same event in the same patient will be counted only once in the tables within a treatment category. The denominator for computation of percentages is the safety population within each treatment category. In all AE incidence tables, the total patient years (in the unit of 100 patient-years) for each treatment category and overall (see Section 2.3.2) will be presented in the corresponding column headers.

The number of events per 100 patient-years (adjusted for the total duration of exposure) by the treatment category and overall (see Section 2.3.2) will be presented for each AESI during the treatment-emergent period.

The table of all treatment-emergent adverse events presented by SOC and PT will be sorted by the internationally agreed SOC order (from MedDRA) and decreasing frequency of PTs within SOCs. Sorting will be based on the results for the overall patients across treatment categories, unless otherwise specified.

Analysis of all treatment-emergent adverse events

The following treatment-emergent adverse event summaries by the treatment category and overall patients (see Section 2.3.2) will be generated for the safety population. Sorting will be based on the results for the overall patients across treatment categories, unless otherwise specified.

- Overview of treatment-emergent adverse events, summarizing number (%) of patients (including total patient years in column headers) with any
 - Treatment-emergent adverse event
 - Treatment-emergent serious adverse event
 - Treatment-emergent adverse event leading to death
 - Treatment-emergent adverse event leading to permanent treatment discontinuation
- All treatment-emergent adverse events by primary SOC, HLGT, HLT, and PT, showing number (%) of patients (including total patient years in column headers) with at least one treatment-emergent adverse event sorted by the SOC internationally agreed order. The other levels (HLGT, HLT, PT) will be sorted in alphabetical order.
- All treatment-emergent adverse events by primary SOC and PT, showing the number (%) of patients (including total patient years in column headers) with at least one treatment-emergent adverse event, will be presented by the internationally agreed SOC order and by decreasing incidence of PTs within each SOC.
- All treatment-emergent adverse events by primary SOC, showing the number (%) of patients (including total patient years in column headers) with at least one treatment-emergent adverse event, will be presented by the internationally agreed SOC order.
- All possibly drug-related TEAEs by primary SOC and PT, showing number (%) of patients (including total patient years in column headers) with at least one TEAE, will be presented by SOC internationally agreed order and by decreasing incidence of PTs within each SOC.
- All TEAEs by maximal severity, presented by primary SOC and PT, showing the number (%) of patients (including total patient years in column headers) with at least one TEAE by severity (ie, mild, moderate, or severe), sorted by the order defined above.

• Number (%) of patients (including total patient years in column headers) experiencing TEAE(s) presented by primary and secondary SOC, HLGT, HLT, and PT sorted by SOC internationally agreed order. The other level (HLGT, HLT, PT) will be presented in an alphabetic order.

Analysis of all treatment emergent serious adverse event(s)

- All treatment-emergent serious adverse events by primary SOC, HLGT, HLT, and PT, showing the number (%) of patients (including total patient years in column headers) with at least one treatment-emergent serious adverse event, will be presented by the internationally agreed SOC order. The other levels (HLGT, HLT, PT) will be presented in alphabetical order.
- All treatment-emergent serious adverse events by primary SOC and PT, showing number (%) of patients (including total patient years in column headers) with at least one TEAE, will be presented by SOC internationally agreed order and decreasing incidence of PTs within SOC.

Analysis of all treatment-emergent adverse event(s) leading to treatment discontinuation

- All TEAEs leading to treatment discontinuation, by primary SOC, HLGT, HLT, and PT, showing the number (%) of patients (including total patient years in column headers) will be presented by the internationally agreed SOC order. The other levels (HLGT, HLT, PT) will be presented in alphabetical order.
- All TEAEs leading to treatment discontinuation, by primary SOC and PT, showing number (%) of patients (including total patient years in column headers) with at least one TEAE, will be presented by SOC internationally agreed order and by decreasing incidence of PTs within each SOC.

Analysis of adverse events of special interest (AESI) and other selected AE groupings

Summaries of AESI defined by the search criteria:

- All treatment emergent AESIs and other selected AE groupings identifiable by MedDRA terms or by laboratory values (as in ALT elevation), by AESI category and PT, showing the number (%) of patients (including total patient years in column headers), will be presented by decreasing incidence of PT within each AESI category.
- An overview summary within each treatment-emergent AESI and other selected AE groupings will include:
 - Number (%) of patients with any TEAE
 - Number (%) of patients with any SAE (regardless of treatment-emergent status)
 - Number (%) of patients with any treatment-emergent SAE
 - Number (%) of patients with any AE leading to death

- Number (%) of patients with any TEAE leading to permanent treatment discontinuation
- Number (%) of patients with any TEAE by maximum intensity, corrective treatment, and final outcome
- Number (%) of patients with any possibly related TEAE
- Kaplan-Meier plot (cumulative incidence (%) versus time up to Week 60 based on K-M estimate) for time-to-onset of the first TEAE
- Cumulative incidence (K-M estimates) up to specified time points (Week 4, Week 12, Week 24, Week 48, Week 60)

Notes for the last two bullets: when TEAE start date or worsening date is partially available, the maximum of the earliest possible TEAE start date and the treatment start date will be used. When TEAE start date or worsening date is completely missing, the treatment start date will be used.

• Number of treatment-emergent AESIs and other selected AE groupings per 100 patientyears (total number of events adjusted for the total duration of exposure) will be presented by decreasing incidence of PT within each AESI and other selected AE groupings category.

Analysis of pre-treatment adverse events

- All pre-treatment AEs by primary SOC and PT, showing the number (%) of patients (including total patient years in column headers) with at least one pre-treatment AE, will be presented by the internationally agreed SOC order and by decreasing incidence of PTs within each SOC.
- All pre-treatment SAEs by primary SOC and PT, showing the number (%) of patients (including total patient years in column headers) with at least one pre-treatment SAE, will be presented by the internationally agreed SOC order and by decreasing incidence of PTs within each SOC.
- All pre-treatment adverse events leading to study discontinuation by primary SOC and PT, showing the number (%) of patients (including total patient years in column headers), will be presented by the internationally agreed SOC order and by decreasing incidence of PTs within each SOC.

Analysis of adverse events

• All pre-treatment, treatment-emergent, or post-treatment-emergent AEs by primary SOC and PT, showing the number (%) of patients (including total patient years in column headers) with at least one AE, will be presented by the internationally agreed SOC order and by decreasing incidence of PTs within each SOC.

